**Effect of esketamine on perioperative depressive symptoms
in major surgery patients (PASSION II)**

STUDY PROTOCOL

Protocol Version 2.0

Version Date: 20/01/2021

NCT number: NCT04425473

Prepared by statistician: [name]

Approved by Principal Investigator: [name]

Effect of esketamine on perioperative depressive symptoms in major surgery patients (PASSION II): study protocol for a randomized controlled trial

Introduction

Depression is a common mental disorder that has been the primary risk of disability and is an important risk factor associated with a high burden of disease; it is estimated that more than 300 million people suffer worldwide.¹⁻² Patients undergoing major surgery may have depressive symptoms induced by stress reactions, which could affect mental health in the surgery population. Depressive symptoms are characterized by loss of interest and low mood,—during the perioperative period. Although depressive symptoms are different from depression disorder, they could also lead to worse clinical outcomes after surgery, such as cognitive dysfunction, delirium, pain, and even shortened survival time.³⁻⁶ It has been reported that more than 24% of patients have depressive symptoms during the perioperative period, and this figure is nearly 44% in patients undergoing cardiac surgery or neurosurgery.⁶⁻⁹ However, few interventions resolve the depressive symptoms that occur during the perioperative period, and the influence of antidepressant effects in the early stage on prognosis in the future remains controversial.

Ketamine, a classic anaesthetic for sedation and analgesia, has been reported that could take rapid antidepressant effects in depression patients.¹⁰ However, the benefit of ketamine administration in patients with depressive symptoms undergoing major surgery is inconsistent.¹¹⁻¹³ To address this problem, our research team developed the PASSION study to explore the effect of ketamine on depressive symptoms in the neurosurgery population.¹⁴ In the 84 participants that were enrolled, we found that ketamine improved depressive symptoms at the third postoperative day, and the response rate was higher in the ketamine group than in the placebo group (41.5% vs. 16.3%), and no adverse events occurred. However, there were several limitations in the PASSION study; for example, the degree of remission did not reach desired levels chiefly because of the relatively small sample size, a single type of surgery was

involved in the trial, and esketamine has been gradually substituted for ketamine in clinical practice.

Esketamine is a racemic compound of ketamine that has been reported to have rapid and marked antidepressant effects.¹⁵ Based on studies with ketamine, esketamine was developed and has been used for major depression patients since the Food and Drug Administration approved its use in 2019. Compared with traditional antidepressants, which require more than one week to take effect in depression patients, esketamine shortens the reaction period to nearly 1 hour after administration with few adverse effects, and the use of esketamine nasal spray has become a novel antidepressant for treatment-resistant depression patients.¹⁶ Compared with ketamine, esketamine shows similar pharmacological characteristics but less side-effect. However, the effects of esketamine administration on depressive symptoms are still unknown. Thus, we should make further efforts to determine the effect of esketamine on depressive symptoms in major surgery patients.

Safety issues associated with the administration of esketamine during surgery are also unclear. It is reported that ketamine could change the intracranial pressure and hemodynamics during drug administration, and increase the risk of psychotic symptoms, hallucinations, or nausea and vomiting after major surgery. For repeated application, ketamine was reported associated with drug abuse and may interact with bladder urothelial cells and induce apoptosis.¹⁷ Due to esketamine and ketamine having similar pharmacological effects, whether the harmful effect mentioned above for single administration of esketamine in major surgery patients is not known for certain.

Based on the previous studies, the depressive symptoms may be a temporary state because of the stress by operation or diseases. Thus, we conducted this trial to explore the effectiveness of esketamine used in surgery patients with depressive symptoms. It is hypothesized that the administration of esketamine intravenously will improve the depressive symptoms in the major surgery population. The primary endpoint is the remission rate at postoperative day 3, and the secondary endpoints consist of other effectiveness and safety-related parameters.

Methods and analysis

Trial design

This study is a multicenter randomized controlled clinical trial to explore the effect of esketamine on depressive symptoms screened during the perioperative period (the flow chart see figure 1). It was approved by the Institutional Review Board of Beijing Tiantan Hospital, Capital Medical University, Beijing, China (KY-2020-058-02). All participants or their legal representatives will provide written informed consent after screening and before randomization. Registration information has been supplied on clinicaltrials.gov (NCT04425473).

Participants

The study will be conducted at medical centres in China, and training of the study protocol will be held regularly to guarantee the quality of the trial. Major surgery patients who are 18 to 65 years old with moderate to severe depressive symptoms will be included after informed consent is obtained from their legal representative. Moderate to severe depressive symptoms are defined as Patient Health Questionnaire 9 (PHQ-9)^{18 19} scores equal to or more than 10 and Montgomery-Åsberg Depression Rating Scale (MADRS) scores equal to or more than 22.²⁰ Major surgery is defined as an elective operation with an estimate of more than 2 hours and includes neurosurgical tumour resection, coronary artery bypass grafting operation, total hip or knee arthroplasty surgery, breast cancer surgery, pneumonectomy, or hepatectomy. Patients with any of the following will be excluded: aphasia or other conditions that may lead to the inability for mental assessments; diseases requiring maintenance of intubation after surgery; history of psychotic or bipolar disorder; primary diseases that could change hormone levels with laboratory evidence; body mass index more than 30 kg/m²; Child-Pugh grade B or C (defined as Child-Pugh scores more than 6 points); history of antidepressant therapy in the 2 weeks before screening; repeated suicide attempts (evaluated by a score equal to or more than 3 on the 12-item Quick Inventory of Depressive Symptomatology); history of adverse events to ketamine or esketamine; history of drug use disorder; or current pregnancy or breastfeeding.

Randomization and grouping

Participants will be randomly assigned to the esketamine group or placebo group at a 1:1 ratio. Randomization results will be achieved via a real-time, online system before surgery. A randomized four-blocks design stratified patients by depressive severity (severe depressive symptoms are defined by MADRS scores equal to or more than 30). The randomization sequence was created by independent engineers who will keep the allocation blind, and all study-related investigators will be blinded to the randomization results.

Intervention and anaesthesia management

All participants included in this study will receive trial drugs intravenously when the incision is being sutured. In the esketamine group, patients will be administered a total dose of 0.2 mg/kg esketamine (Hengrui Induction, Jiangsu, China) over 40 mins. Patients in the placebo group will receive an equivalent volume of normal saline at the same speed. Patients in this study will be under general anaesthesia for major surgery. Anaesthesia management will follow the standard procedure. Total intravenous anaesthesia or balanced anaesthesia will be implemented to maintain appropriate levels of sedation, analgesia, and muscle relaxation. Anaesthetics are administered at appropriate dosages based on consideration of the clinical anaesthetists and will include sedatives (propofol or etomidate), analgesics (sufentanil or remifentanil), muscle relaxants (rocuronium or cisatracurium), or inhaled anaesthetics (sevoflurane). Patient-controlled analgesia devices will be applied after surgery by using sufentanil and ondansetron to maintain numerical rating scale scores equal to or less than 4. Other analgesics could be used with the occurrence of severe pain (numerical rating scale score more than 7) during the postoperative period.

Blinding

The trial drugs will be prepared by an independent person who is not participating in screening, intervention, and follow-up procedures (see figure 2). Esketamine will be diluted to a concentration of 0.5 mg/ml with normal saline. Both esketamine and normal saline will be kept in syringes (50 ml) with the same appearance and labelled with "the trial drugs, randomization code". The participants will receive the trial drug at a speed of 0.6 ml/h per kilogram of weight for 40 min. The intervention will be completed by

the anaesthesiologists in charge of the surgery. The anaesthesiologists, accessors, and patients will be blinded to the type of drug administered during surgery. The administered drug will be unmasked, with the agreement of the primary investigator, when esketamine-related severe adverse events occur (such as an allergy to the study drug) after the intervention and before the termination of surgery.

Outcomes

The primary outcome is the proportion of participants attaining remission (defined as a MADRS score less than or equal to 10) three days after surgery, based on an evaluation by blinded accessors at the bedside.

Secondary outcomes, including the differences in MADRS scores at three days and five days (or discharge) after surgery and the rates of patients achieving a response (MADRS scores reduced to or lower than half of the baseline MADRS score), the rate of severe pain within 72-hour postoperative period (severe pain is defined by the numeric rating scale pain scores equal to or more than 7).²¹

Safety outcomes include manic symptoms evaluated by the 11-item Young Mania Rating Scale (defined by YMRS scores more than or equal to 5) within the 3-day postoperative period,²² psychotic symptoms measured by a nonzero score on four particular items of the Brief Psychiatric Rating Scale (unusual thought content, suspiciousness, hallucinations, and conceptual disorganization) during the three days after surgery,^{23, 24} dissociative symptoms accessed by a nonzero score on the Clinician-Administered Dissociative States Scale within three days after the operation,²⁵ and all drug-related adverse events during surgery or before discharge.

Data management

The clinical data will be recorded and managed with the electronic database. The paper version materials including the protocol, the case reported forms, informed consent forms, and electronic version database will be preserved by the primary investigator and stored in the independently locked strongbox in Beijing Tiantan Hospital.

Sample size calculation

It has been reported that the remission rate difference in the antidepressant effects between esketamine and ketamine was 3.8% in treatment-resistant depression

patients.²⁶ In the perioperative population with depressive symptoms, the remission rate was reported to be 23.1% in the ketamine group and 9.3% in the placebo group based on the PASSION study at our research site. We assumed that the remission rate in the esketamine group will be 19.3% and that in the placebo group will be 10%. A sample size of 506 participants will provide 80% power to show the difference between the esketamine group and the placebo group (with a ratio of 1:1), including 1 interim analysis by using a 2-sided significance level of 0.05.²⁷ With the consideration of a 10% attrition rate, the total sample size is planned to be 564.

Interim analysis

The planned interim analysis will be performed after 424 patients (75% of the total sample size) completed the follow-up. This interim analysis will be based on the ITT principle, and the P value will be set at 0.019 following adjustment by O'Brien-Fleming methods.²⁸

Statistical analysis

Continuous variables will be reported as the mean (standard deviation) for normally distributed data and the median (interquartile ranges) for skewed distributions. Categorical variables will be reported as the number (proportion), and the relative risk with its 95% confidence intervals will be calculated. The difference between groups will be reported with 95% confidence intervals of absolute differences calculated by independent t-tests for continuous variables and using the Hodges–Lehmann method for skewed variables. The primary endpoint of remission rate at 3 days after surgery will be analyzed by using the chi-square test or Fisher's exact test. The secondary outcomes will be analyzed using t-tests, Mann–Whitney U tests, and chi-square or Fisher's exact tests as appropriate. The adjusted odds ratios will be estimated by using a logistic regression model by taking into account the unbalanced baseline variables, age, sex, the severity of depressive symptoms, and pain severity after surgery.

For missing values, both imputations with the mean or median or the last observed assessment and multiple imputations will be applied. Sensitivity analysis for different imputation plans will be used to explore the statistical nature of the missing data. All statistical tests will be 2-sided at a significance level of 0.05 and the effect sizes will

also be reported. Because of the potential for type I errors due to the lack of adjustment for multiple comparisons, the findings for secondary outcomes or sensitivity analyzed should be interpreted as exploratory. All analyses will be performed by using Stata version 14.0.

Safety consideration

Once adverse events occurred during drug intervention, the principal investigator will be informed immediately. Based on the severity of the adverse events and the relation to esketamine, the unmasking process will be considered by the principal investigator. All the adverse events that occurred during the trial will be recorded in detail and closely monitored until stabilization or the time of the study intervention is not the cause for adverse events. All the adverse events will be reported to the Institutional Review Board by the principal investigator.

Patient and public involvement

Patients and the public were not involved in the trial design. Participants will have access to the findings of the study on request.

Ethics and dissemination

This study was approved by the Institutional Review Board of Beijing Tiantan Hospital, Capital Medical University, Beijing, China on October 30, 2020 (KY-2020-058-02). It has been registered on clinicaltrials.gov on June 11, 2020 (NCT04425473). The first participant was recruited on February 19, 2021. The conclusions of this study will be published in peer-reviewed journals.

Discussion

This study is a randomized placebo-controlled double-blinded clinical trial that aims to explore the effect of esketamine on depressive symptoms in the major surgery population. The participants will be administered 0.2 mg/kg esketamine intravenously within 40 min with the suturing of the incision. The efficacy and safety endpoints will be observed during the perioperative period and in the long term after major surgery.

In this study, the patients in the control group will receive normal saline rather than other antidepressants. To our knowledge, traditional antidepressants need to be administrated continuously for more than one week before taking effect, which is not suitable for short hospital stays in surgery patients. Besides, traditional antidepressants, such as selective serotonin reuptake inhibitors and tricyclic antidepressants, may lead to a potential risk for bleeding, arrhythmia, and anaesthetic metabolism dysfunction during surgery.²⁹ For ethical concerns, the participants enrolled in this study will be provided with a professional consultation from the psychiatrist as necessary.

Although the PASSION study found that ketamine could alleviate the depressive symptoms assessed by clinician-rating scales to some extent in neurosurgery patients, there are still several concerns about the evidence of clinical trials regarding the resolution for depressive symptoms in the surgery population. First, screening standards for depressive symptoms during the perioperative period are lacking, and assessments in different depressive populations may affect the results of studies. Minor depressive symptoms may induce few adverse outcomes and disappear spontaneously after surgery. However, moderate-to-severe depressive symptoms could lead to worsening moods, enhanced postoperative pain, or suicidal ideation, and there is an urgent need to resolve these symptoms. Second, the rating scale tools are subjective. Self-rating scales have commonly been used in previous studies, which also require clinician-rating scales to verify the antidepressant effects. Third, small sample size may have led to false-positive or false-negative results in previously reported studies. Fourth, the long-term effects of ketamine or esketamine on depressive symptoms in patients undergoing major surgery remain unclear. Meanwhile, whether the analgesic effect of esketamine is the key factor considering the antidepressant effects needs to be investigated.

The safety of esketamine as an antidepressant in the context of surgery is unknown. Esketamine, as a novel drug for replacing ketamine, is not approved for intravenous use as an antidepressant. The plasma concentration for the antidepressant dosage of ketamine was reported to be approximately 70–200 ng/ml, which is far lower than the anaesthetic concentration (2000–3000 ng/ml).¹⁰ It is essential to explore an appropriate and safe dosage of esketamine for antidepressant treatment during surgery. Esketamine used in patients undergoing general anaesthesia is theoretically safer than the administration in awake patients. However, different anaesthetics administered during general anaesthesia may induce synergic effects with esketamine or attenuate treatment effectiveness. Thus, it is important to monitor the quality of recovery from general anaesthesia. Similar to ketamine, which could lead to psychotic symptoms, hallucinations, manic symptoms, or dissociative symptoms, esketamine given at an antidepressant dosage may also increase these risks after surgery. Determining the safe dosage will also be important for the popularization of esketamine used as an antidepressant during the perioperative period. Based on the previous study, both 0.2 mg/kg and 0.4 mg/kg of esketamine administrated intravenously were reported with remarkable anti-depression effects and low-dose of esketamine (0.2 mg/kg) with fewer side-effects rate than high-dose of esketamine after drug administration.¹⁵ Thus, we selected 0.2 mg/kg of esketamine as the intervention dosage in this study.

In summary, this study is a randomized controlled trial focusing on the mental health of perioperative patients. The expected result is that esketamine could markedly improve the remission rate after surgery without obvious adverse events, and long-term outcomes may also benefit from the administration of esketamine.

Footnotes

Funding: This study was supported by Beijing Municipal Science & Technology Commission (No. Z191100006619067) and Beijing Municipal Administration of Hospitals Clinical Medicine Development of Special Funding Support (DFL20180502).

Conflicts of interest: The authors declare no competing interests.

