**Effect of esketamine on perioperative depressive symptoms
in major surgery patients (PASSION II)**

STATISTICAL ANALYSIS PLAN

Protocol Version 2.0

Version Date: 15/03/2024

NCT number: NCT04425473

Prepared by statistician: [name]

Approval by Principal Investigator: [name]

Document Version History

Version Date	Version	Author	Change Description
05/04/2022	1.0	[name]	Initial release
15/03/2024	2.0	[name]	Final version

TABLE OF CONTENTS

Introduction	4
Study objective and endpoints.....	4
Study overview	5
Statistical hypotheses.....	7
Sample size determination	7
Interim analysis.....	7
Population analyzed	8
Statistical considerations	8
Statistical analysis.....	9
Reference	15

1. Introduction

This statistical analysis plan (SAP) explains the established statistical analyses for a multicenter, randomized, placebo-controlled study (the PASSION II study) to evaluate the impact of esketamine on moderate-to-severe depressive symptoms in major surgery patients. This SAP is in accordance with the published protocol ^[1] (Zhou et al., Effect of esketamine on perioperative depressive symptoms in major surgery patients (PASSION II): study protocol for a randomized controlled trial. *BMJ Open* 2022;12: e056713. DOI:10.1136/bmjopen-2021-056713), together with any following amendments.

This SAP is special for the use of research members within Beijing Tiantan Hospital and should be implemented in combination with the PASSION II protocol. This SAP was written by the Principal Statistician and approved by the Principal Investigator. Additional statistical analysis not planned in the protocol will be performed and considered carefully in line with the principles of this analysis plan.

2. Study objective and endpoints

Study objective

The primary objective of this study is to assess the effects of esketamine administered intraoperatively at 0.2 mg/kg within 40 min versus an equal speed of placebo on 3-day depressive symptoms after intervention in patients with depressive symptoms patients undergoing major surgery.

All the secondary objectives in the protocol will be exploratory and list as follows:

To assess the effectiveness of esketamine administrated for depressive symptoms during the perioperative period.

Other objectives are as follows:

To compare moderate-to-severe pain after ketamine and placebo were administered during the first 3 postoperative days.

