To compare all the safety events of surgery and study drugs administered intraoperatively in terms of psychiatric symptoms, dissociative symptoms and manic

symptoms, and adverse and serious adverse events during the study period. Further exploratory objectives were to evaluate the postoperative 1-, 3-, and 6-month quality of life (WHODAS 2.0) and depressive symptoms.

Study endpoints

Primary efficacy

The remission rate of depressive symptoms at 3 days postoperatively was defined as a Montgomery-Åsberg Depression Rating Scale (MADRS) score less than or equal to 10. [2]

Secondary efficacy

The remission rate of depressive symptoms at discharge was defined as MADRS scores less than or equal to 10.

The response rates of depressive symptoms 3 days after surgery and at discharge.

The rate of moderate-to-severe pain during the first postoperative 3 days and severe pain were defined as numeric analogue scale (NAS) scores greater than 3.

Changes in further efficacy: Changes in depressive symptom scores at 1 month, 3 months, and 6 months postoperative; and the WHODAS 2.0.

Safety efficacy

Psychiatric complications: drug-related manic, psychotic, and dissociative symptoms during the first 3-day postoperative period. [3,4]

Surgery-related complications

3. Study overview

This study is a multicenter, randomized, placebo-controlled and double-blinded clinical trial. The primary null hypothesis of this study is that there is no difference in the 3-day postoperative remission rate between 0.2 mg/kg esketamine administered intraoperatively for 40 min and placebo administered at the same time in the same volume.

Patients undergoing major surgery, combined with moderate-to-severe depressive symptoms defined as those with a Patient Health Questionnaire 9 (PHQ-9) [5] score

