The intent-to-treat (ITT) population will include all the subjects after randomization and who received esketamine or placebo during surgery. After randomization, it is assumed that all participants have been administered a placebo or esketamine. The modified intent-to-treat population will be excluded from the analysis after randomization situations no longer meet the eligibility criteria, patients who do not have surgery, or patients who cannot undergo follow-up due to surgery-related complications, such as aphasia or coma. The modified ITT population will be tested for demographic characteristics and efficacy and safety outcomes. The population will be used for primary analysis of the efficacy and safety outcomes.

Per-Protocol population

The per protocol (PP) population will comprise all participants except subjects who are confirmed as protocol transgressors. The subjects excluded from the PP population will be confirmed before being blind. This population was used for sensitivity analysis to determine the effect of missing data. In the PP population, subjects will be analysed according to the treatment received and the real events after postoperative assessments.

8. Statistical considerations

The data will be analyzed by Stata 16.0 software (Stata Corp LP, College Station, TX,

USA) and all significance tests will be two-sided, with an alpha setting of 0.05 and 95% confidence intervals confirmed.

Subgroup analysis

The rate of postoperative 3-day remission will be presented at each level of the variables listed below. The degree of change in the treatment effect of each subgroup at different levels will be evaluated via an interaction test.

Multiplicity

The single primary outcome was defined in the protocol, and all other efficacy variables were treated as secondary or other. The only comparison of interest in this study was between esketamine and placebo, and there was no need to adjust for multiple comparisons. All estimates of treatment effects for secondary endpoints will be presented with 95% confidence intervals, no inferential tests will be performed, and only exploratory tests with simple descriptions of these endpoints will be performed.

Missing Data

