The remission rate of depressive symptoms at 3 days postoperative will be summarized by treatment group via the chi-square test or Fisher's exact test to compare the differences between groups in the m-ITT population. The risk ratio for the intervention comparison is presented, and the 95% CI is reported. The results are

also displayed graphically on a histogram plot.

Secondary efficacy analysis

All secondary endpoints are based on the m-ITT population. For categorical variables, which are presented as frequency counts and percentages, a two-sided Pearson's χ^2 test or Fisher's exact test will be used, as appropriate. The odds ratios and 95% CIs were calculated. For continuous variables, prior to performing the statistical analysis, the assumptions of normality and homogeneity of variance of the residuals of quantitative variables were tested via the Shapiro-Wilk test and Levene's test, respectively. For efficacy analysis, a t test (normal variables) or the Mann-Whitney U test (skewed variables) will be used, as appropriate. The absolute difference and 95% CIs were calculated via the Mann-Whitney U test and the Hodges-Lehmann method.

Safety analysis

Safety endpoints will be assessed in the total population. The related variables are presented as frequency counts and percentages in both the esketamine group and the control group, odds ratios and 95% CIs.

Interaction with subgroups

A summary forest plot will be presented on the basis of the predefined subgroups, and interactions between them will be investigated for the primary endpoint. Exploratory subgroup-specific summary statistics and p values for interactions are presented. A separated logistic model was applied for interaction to identify its effect significance. The subgroup analysis included the following covariates: unbalanced baseline variables, age, sex, severity of depressive symptoms and pain severity after surgery.

Main results with Tables

Table 1. Demographic and preoperative characteristics of the total population.

Characteristics	Esketamine group	Control group
Sex		
Female	n (%)	n (%)
Male	n (%)	n (%)
Age, yr,	Mean (SD)/median (IQR)	Mean (SD)/median (IQR)
Height, cm,	Mean (SD)/median (IQR)	Mean (SD)/median (IQR)
Weight, kg,	Mean (SD)/median (IQR)	Mean (SD)/median (IQR)
Education	n (%)	n (%)
Married	n (%)	n (%)
Living state (alone)	n (%)	n (%)
Employed	n (%)	n (%)
Currently smoke	n (%)	n (%)
Alcohol intake		
Never	n (%)	n (%)
Occasional	n (%)	n (%)

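### Pain after surgery, measured after the infusion and itself a trial outcome, is used as an adjustment covariate and a subgroup variable, so the adjusted odds ratio can be biased for the total effect of esketamine

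*Protocol*

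**What the plan says.** The primary test of 3-day remission is an unadjusted chi-square or Fisher test in both documents, with a risk ratio. Beyond that:

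- **Adjusted model.** The Protocol, Statistical analysis, plans odds ratios from a "logistic regression model by taking into account the unbalanced baseline variables, age, sex, the severity of depressive symptoms, and pain severity after surgery". It does not name the outcome of the model.
- **Subgroups.** SAP section 8 says "The rate of postoperative 3-day remission will be presented at each level of the variables listed below". The only list that follows is in section 9, Interaction with subgroups: "The subgroup analysis included the following covariates: unbalanced baseline variables, age, sex, severity of depressive symptoms and pain severity after surgery".
- **Timing.** Protocol, Intervention and anaesthesia management: "All participants included in this study will receive trial drugs intravenously when the incision is being sutured".
- **Pain as an outcome.** The Protocol's secondary outcomes include "the rate of severe pain within 72-hour postoperative period" (score 7 or more). SAP section 2 has "The rate of moderate-to-severe pain during the first postoperative 3 days" (score above 3).
- **Pain as a mechanism.** The Protocol's Discussion says that "whether the analgesic effect of esketamine is the key factor considering the antidepressant effects needs to be investigated". The same section says that depressive symptoms can worsen postoperative pain.
- **Standing of the two documents.** SAP section 1 says that the SAP "should be implemented in combination with the PASSION II protocol".

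Neither document describes a mediation analysis or labels the adjusted odds ratio as a direct effect.

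**The concern.** Covariate adjustment in a randomised trial keeps its simple reading only if treatment cannot change the covariates. Age, sex and baseline severity meet that condition. Pain after surgery does not, because it is measured once the drug has been started and the trial itself tests whether the drug changes it.

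Two things can go wrong. If esketamine relieves pain and pain hinders remission, adjusting for pain removes part of the effect the trial is meant to measure. If pain and remission share causes, comparing arms at the same pain level compares different kinds of patient, even if pain itself does nothing to mood. The Protocol's Discussion gives grounds for both.

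At stake are the supportive adjusted odds ratio and one exploratory subgroup. A reader who sees an adjusted value below the unadjusted one may take it as a correction of the primary result, when it is at best the part of the effect that does not run through pain. SAP Table 2 adds to the risk: it shows an odds ratio for the primary outcome without saying whether it is adjusted.

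**Working it through.** **Inputs from the documents.** Remission 10% on placebo and 19.3% on esketamine; 506 patients, so 253 per arm; two-sided 5% level.

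**Assumed inputs.** The documents give no pain rates and no association between pain and remission. I take pain as yes/no, 50% on placebo, and vary the reduction on esketamine and the odds ratio of pain on remission.

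**Unadjusted reference.**
- Odds ratio = (0.193/0.807)/(0.10/0.90) = 2.15; log odds ratio 0.767.
- SE = √(1/48.8 + 1/204.2 + 1/25.3 + 1/227.7) = 0.263.
- Chance of p<0.05 = Φ(0.767/0.263 − 1.96) = 83%. This is a single-look Wald figure and serves only as the comparator below. The planned 80% with one interim look is not in question: a continuity-corrected calculation gives 494, and 494 × 1.018 for the interim look is 503, close to 506.

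**Pain-adjusted odds ratio.** Hold the total effect at 10% against 19.3%. In each arm, find the remission rates with and without pain that average to the arm's rate and have the assumed pain odds ratio between them. The treatment odds ratio within pain level follows.

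Example: pain 50% against 30%, pain odds ratio 0.5.
- Placebo: 0.5 × 13.03% + 0.5 × 6.97% = 10.0%.
- Esketamine: 0.7 × 22.22% + 0.3 × 12.50% = 19.3%.
- Without pain: (0.2222/0.7778)/(0.1303/0.8697) = 1.91. By construction it is the same with pain.
- Shift = (ln 2.152 − ln 1.906)/0.263 = 0.46 SE.

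| Pain, placebo vs esketamine | Pain odds ratio on remission | Adjusted odds ratio | Shift in SE | Chance of p<0.05 |
|---|---|---|---|---|
| unadjusted | – | 2.15 | – | 83% |
| 50% vs 45% | 0.6 | 2.11 | 0.1 | 81% |
| 50% vs 40% | 0.5 | 2.03 | 0.2 | 76% |
| 50% vs 30% | 0.5 | 1.91 | 0.5 | 67% |
| 50% vs 20% | 0.25 | 1.57 | 1.2 | 37% |

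Three bounding cases:
- **Drug does not change pain.** The adjusted odds ratio is 2.18 (pain odds ratio 0.5) or 2.24 (0.25). This is ordinary non-collapsibility, not bias.
- **Drug works only through pain.** With pain 50% against 30% and a pain odds ratio of 0.3, remission rises from 10% to 12.0%, but the adjusted odds ratio is exactly 1.00.
- **Shared cause only.** Pain has no effect on remission, but an unmeasured factor triples the odds of pain and cuts the odds of remission to a third. The adjusted odds ratio is 2.10 (50% vs 40%) or 2.04 (50% vs 30%).

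**Pain subgroup.** Assume half the patients have a factor that cuts remission odds to a third. Placebo pain is 60% with it and 40% without. Pain does not affect remission, and the drug's odds ratio on remission is the same with and without the factor.
- Esketamine pain 40% and 20% (a 20-point cut in everyone): odds ratios 2.10 without pain and 1.99 with pain, ratio 0.95.
- Esketamine pain 60% and 10% (relief only in those without the factor): 2.36 and 1.56, ratio 0.66. The apparent interaction comes only from who ends up in each pain level.

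**The case against.** The strongest reply is that nothing confirmatory depends on this. The primary test is unadjusted, no stopping rule uses the adjusted odds ratio, and the Protocol calls secondary and sensitivity findings exploratory, as the SAP does the subgroup statistics. That stands, and it limits the weight of the point. It does not remove it: an exploratory label deals with multiplicity and does not tell the reader that a different quantity is being estimated.

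Second, the SAP is later than the Protocol, its main model has no covariates, and it may simply have moved the list to the subgroup section. This is a fair reading, but the SAP does not withdraw the Protocol's model and says it is to be used with the Protocol. The subgroup use is in the SAP either way. If the SAP's list means adjusters inside the interaction models and not subgroup factors, the same objection applies.

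Third, the effect may be small. Patients receive patient-controlled analgesia, and the Protocol's outcome is severe pain. With an assumed 10% or 20% severe pain on placebo, a 5-point cut and a pain odds ratio of 0.5, the adjusted odds ratio is 2.10, a shift of about 0.1 SE; a 10-point cut from 20% gives 2.04, about 0.2 SE. The 0.66 interaction is a constructed case, and at 253 per arm (SE of the log ratio about 0.56) the test would reject about 11% of the time against a nominal 5%. All this is correct. The bias grows, though, with the strength of the mechanism that the Protocol wants investigated.

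Last, pain may have been included on purpose, to examine that mechanism. If so, the plan should say so and state the assumptions. Listing pain beside age and sex does neither.

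**Conclusion.** The concern holds. Postoperative pain is a post-treatment variable, a secondary outcome and a mechanism named in the Protocol, yet it is listed as an ordinary covariate and subgroup factor. That is certain from the text. The size is not. It depends on how far esketamine changes pain and how pain relates to remission, and neither is given. Across the main assumed scenarios the odds ratio falls from 2.15 to between 2.11 and 1.57, a shift of 0.1 to 1.2 SE; the larger values need a strong effect on pain and a strong link from pain to remission. These figures take 3-day remission as the outcome of the model, which the Protocol does not state. The change should be made, but the primary conclusion of the trial does not rest on it.

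**What to change.** - Delete postoperative pain severity from the covariate list in the Protocol, Statistical analysis, and from the subgroup list in SAP section 9.
- Replace the open-ended reference to imbalanced baseline variables with a short fixed list measured before the infusion: the severity stratum (MADRS 30 or more) or baseline MADRS, age and sex. At the planned rates 253 × (0.10 + 0.193) ≈ 74 remissions are expected, enough for treatment plus three covariates.
- State that the model is for 3-day remission, and say whether the odds ratio in SAP Table 2 is adjusted.
- Do not let delayed extubation or time to spontaneous respiration enter as baseline covariates. SAP section 9 groups them with baseline data, but both follow the start of the infusion.
- Keep postoperative pain as an outcome. If the analgesic route is of interest, add a separately labelled exploratory mediation analysis with its assumptions stated. If a pain subgroup is wanted, chronic pain before surgery is already listed in SAP Table 1.

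The cost is wording in the two documents and the loss of one exploratory subgroup. No new data are needed and the sample size does not change.
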